10.1.3.6. Treatment Visit 3 for all Patients (3 months 12±2 weeks after TV1)

Patients will complete the PD Diary for the 3 consecutive days prior to TV3, and patients will complete the Inhaled Dosing Log daily throughout the treatment period. They will bring their usual PD medications, the PD Diary, Inhaled Dosing Log, used supplies, including empty capsules and inhalers, as well as any unused supplies to the clinic visit. Patients will report to the clinic after having taken their usual PD medications prior to the visit. The timing of administration of the usual morning dose of PD medication may be adjusted by the investigator to accommodate the patient's and/or clinic's schedule. Following their usual morning PD medication, no further non-study PD medications will be used until following completion of all assessments. The timing of arrival should be scheduled to increase the likelihood that patients will be in an ON state upon arrival (i.e., they should arrive to the clinic as shortly as feasible after taking their standard oral PD medications at home).

The following procedures will be done:

- Collect, review, sign, and date the PD Diary and Inhaled Dosing Log.

- Collect used empty capsules and inhalers and unused supplies.
- Confirm that the DLco and spirometry visit at the pulmonary function lab was performed within 2 weeks prior to TV3. If these assessments were not completed prior to the visit, the study visit must be re-scheduled.
- Record any changes in the usual PD medication dose/regimen.
- Record the time that patients took their usual PD medications prior to the visit.
- Record any changes in concomitant medications.
- Patient will complete the PDQ-39, PHQ-9, and PGI-C scale in an ON state.
- Complete the UPDRS Part 2 and S&E ADL scales (preferably in the ON state).
- Complete the UPDRS Part 4 (Questions 32-35 and 36-39) (preferably in the ON state).
- Perform the C-SSRS, Epworth Sleepiness Scale, and QUIP (preferably in the ON state).
- Perform a brief physical examination.
- Record standard vital signs (BP, HR, and RR) and orthostatic vital signs (BP and HR).
- Patient will complete the Impact of Parkinson's OFF Episodes Patient Survey (preferably in an ON state)
- Perform a 12-lead ECG.
- Collect blood for clinical laboratory tests including serum pregnancy test, if applicable. Document fasting status.
- Distribute new study drug kits.
- Review inhaler training with the patient (if needed).
- Distribute the PD Diary and Inhaled Dosing Log and review instructions for completion.
- The patient will remain in the clinic until they go into the OFF state. After confirmation of an OFF state (between 2 and 5 hours after the patient has taken his/her oral PD medication), record the time of the OFF state. Under clinic staff supervision, patients will prepare and self-administer their entire dose of inhaled study drug (CVT-301 DL1 or CVT-301 DL2).
- Observe the patient for the appearance of dyskinesia and note in the source record if the patient experiences dyskinesia at any time within the 60-minute post-dose period. Also, if applicable, record the maximum severity of the dyskinesia.
- Observe the patient for the occurrence of an ON state during the 60-minute post-dose period and note whether this occurs. If the patient converts to the ON state, note whether or not the patient is still in the ON state at 60 minutes post-dose.

- Instruct patients to collect used empty capsules, the PD Diary, Inhaled Dosing Log, and other study supplies and to bring these items to the next visit.
- Monitor patients for AEs throughout the visit.

Upon completion of the 60-minute observations, resumption of normal medications is permitted for the remainder of the day (the patient may use the inhaled study drug 4 more times at home after he/she leaves the clinic on that day if needed for OFF episodes).

The next visit will be scheduled. Clinic staff will also schedule the DLco and spirometry visit within 2 weeks prior to TV4. These assessments should be performed in an ON state (as reported by the patient to the pulmonary technician) in the pulmonary function facility. As part of the procedure, a slow vital capacity maneuver will be first, followed by DLco, and then spirometry. Clinic staff will arrange to speak with patients by telephone 1 week before TV4 to address any concerns or challenges with the inhaler systems, PD Diary, or Inhaled Dosing Log, to monitor for any AEs, to confirm the DLco and spirometry visit at the pulmonary function lab has been done/scheduled, to confirm the next study visit, to ask the patients how many empty study drug kits will be returned at the next visit, and to remind patients of the study procedures required before the next visit (including completion of the PD Diary and Inhaled Dosing Log).

10.1.3.7. Treatment Visit 4 for all Patients (6 months [24±2 weeks] after TV1)

Patients will complete the PD Diary for the 3 consecutive days prior to TV4, and patients will complete the Inhaled Dosing Log daily throughout the treatment period. They will bring their usual PD medications, the PD Diary, Inhaled Dosing Log, used supplies, including empty capsules and inhalers, as well as any unused supplies to the clinic visit.

Patients will report to the clinic after having taken their usual PD medications prior to the visit. The timing of administration of the usual morning dose of PD medication may be adjusted by the investigator to accommodate the patient's and/or clinic's schedule. Following their usual morning PD medication, no further non-study PD medications will be used until following completion of all assessments. The timing of arrival should be scheduled to increase the likelihood that patients will be in an ON state upon arrival (i.e., they should arrive to the clinic as shortly as feasible after taking their standard oral PD medications at home).

The following procedures will be done (also refer to [Section 10.1.4](#) for patients entering the study drug holiday and withdrawal sub-study):

- Collect, review, sign, and date the PD Diary and Inhaled Dosing Log.
- Collect used empty capsules and inhalers and unused supplies.
- Confirm that the DLco and spirometry visit at the pulmonary function lab was performed within 2 weeks prior to TV4. If these assessments were not completed prior to the visit, the study visit must be re-scheduled.
- Record any changes in the usual PD medication dose/regimen.
- Record the time that patients took their usual PD medications prior to the visit.
- Record any changes in concomitant medications.
- Patient will complete the PDQ-39, PHQ-9, and PGI-C scale in an ON state.

- Complete the UPDRS Part 2 and S&E ADL scales (preferably in the ON state).
- Complete the UPDRS Part 4 (Questions 32-35 and 36-39) (preferably in the ON state).
- Perform the C-SSRS, Epworth Sleepiness Scale, and QUIP (preferably in the ON state).
- Perform a full physical examination.
- Record standard vital signs (BP, HR, and RR) and orthostatic vital signs (BP and HR).
- Patient will complete the Impact of Parkinson's OFF Episodes Patient Survey (preferably in an ON state)
- Perform a 12-lead ECG.
- Collect blood for clinical laboratory tests including serum pregnancy test, if applicable. Document fasting status.
- Distribute new study drug kits for patients not entering the study drug holiday.
- Review inhaler training with the patient (if needed) for patients not entering the study drug holiday.
- Distribute the PD Diary and Inhaled Dosing Log and review instructions for completion for patients not entering the study drug holiday.
- The patient will remain in the clinic until they go into the OFF state. After confirmation of an OFF state (between 2 and 5 hours after the patient has taken his/her oral PD medication), record the time of the OFF state. Under clinic staff supervision, patients will prepare and self-administer their entire dose of inhaled study drug (CVT-301 DL1 or CVT-301 DL2).
- Observe the patient for the appearance of dyskinesia and note in the source record if the patient experiences dyskinesia at any time within the 60-minute post-dose period. Also, if applicable, record the maximum severity of the dyskinesia.
- Observe the patient for the occurrence of an ON state during the 60-minute post-dose period and note whether this occurs. If the patient converts to the ON state, note whether or not the patient is still in the ON state at 60 minutes post-dose.
- Instruct patients to collect used empty capsules, the PD Diary, Inhaled Dosing Log, and other study supplies and to bring these items to the next visit for patients not entering the study drug holiday.
- Monitor patients for AEs throughout the visit.

Upon completion of the 60-minute observations, resumption of normal medications is permitted for the remainder of the day (the patient may use the inhaled study drug 4 more times at home after he/she leaves the clinic on that day if needed for OFF episodes for patients not entering the study drug holiday).

The next visit will be scheduled. Clinic staff will also schedule the DLco and spirometry visit at the pulmonary function lab within 2 weeks prior to TV5. These assessments should be performed in an ON state (as reported by the patient to the pulmonary technician) at the pulmonary function facility. As part of the procedure, a slow vital capacity maneuver will be performed, followed by DLco, and then spirometry. Clinic staff will arrange to speak with patients by telephone 1 week before TV5 to address any concerns or challenges with the inhaler systems, PD Diary, or Inhaled Dosing Log, to monitor for any AEs, to confirm the DLco and spirometry visit at the pulmonary function lab has been done/scheduled, to confirm the next study visit, to ask the patients how many empty study drug kits will be returned at the next visit, and to remind patients of the study procedures required before the next visit (including completion of the PD Diary and Inhaled Dosing Log).

10.1.3.8. Treatment Visit 5 for all Patients (9 months [36±2 weeks] after TV1)

Patients will complete the PD Diary for the 3 consecutive days prior to TV5, and patients will complete the Inhaled Dosing Log daily throughout the treatment period. They will bring their usual PD medications, the PD Diary, Inhaled Dosing Log, used supplies, including empty capsules and inhalers, as well as any unused supplies to the clinic visit.

Patients will report to the clinic after having taken their usual PD medications prior to the visit. The timing of administration of the usual morning dose of PD medication may be adjusted by the investigator to accommodate the patient's and/or clinic's schedule. Following their usual morning PD medication, no further non-study PD medications will be used until following completion of all assessments. The timing of arrival should be scheduled to increase the likelihood that patients will be in an ON state upon arrival (i.e., they should arrive to the clinic as shortly as feasible after taking their standard oral PD medications at home).

The following procedures will be done (also refer to [Section 10.1.4](#) for patients entering the study drug holiday and withdrawal sub-study):

- Collect, review, sign, and date the PD Diary and Inhaled Dosing Log.
- Collect used empty capsules and inhalers and unused supplies.
- Confirm that the DLco and spirometry visit at the pulmonary function lab was performed within 2 weeks prior to TV5. If these assessments were not completed prior to the visit, the study visit must be re-scheduled.
- Record any changes in the usual PD medication dose/regimen.
- Record the time that patients took their usual PD medications prior to the visit.
- Record any changes in concomitant medications.
- Patient will complete the PDQ-39, PHQ-9, and PGI-C scale in an ON state.
- Complete the UPDRS Part 2 and S&E ADL scales (preferably in the ON state).
- Complete the UPDRS Part 4 (Questions 32-35 and 36-39) (preferably in the ON state).
- Perform the C-SSRS, Epworth Sleepiness Scale, and QUIP (preferably in the ON state).

- Perform a brief physical examination.
- Record standard vital signs (BP, HR, and RR) and orthostatic vital signs (BP and HR).
- Patient will complete the Impact of Parkinson's OFF Episodes Patient Survey (preferably in an ON state)
- Perform a 12-lead ECG.
- Collect blood for clinical laboratory tests including serum pregnancy test, if applicable. Document fasting status.
- Distribute new study drug kits for patients not entering the study drug holiday.
- Review inhaler training with the patient (if needed) for patients not entering the study drug holiday.
- Distribute the PD Diary and Inhaled Dosing Log and review instructions for completion for patients not entering the study drug holiday.
- The patient will remain in the clinic until they go into the OFF state. After confirmation of an OFF state (between 2 and 5 hours after the patient has taken his/her oral PD medication), record the time of the OFF state. Under clinic staff supervision, patients will prepare and self-administer their entire dose of inhaled study drug (CVT-301 DL1 or CVT-301 DL2).
- Observe the patient for the appearance of dyskinesia and note in the source record if the patient experiences dyskinesia at any time within the 60-minute post-dose period. Also, if applicable, record the maximum severity of the dyskinesia.
- Observe the patient for the occurrence of an ON state during the 60-minute post-dose period and note whether this occurs. If the patient converts to the ON state, note whether or not the patient is still in the ON state at 60 minutes post-dose.
- Instruct patients to collect used empty capsules, the PD Diary, Inhaled Dosing Log, and other study supplies and to bring these items to the next visit for patients not entering the study drug holiday.
- Monitor patients for AEs throughout the visit.

Upon completion of the 60-minute observations, resumption of normal medications is permitted for the remainder of the day (the patient may use the inhaled study drug 4 more times at home after he/she leaves the clinic on that day if needed for OFF episodes for patients not entering the study drug holiday).

The next visit will be scheduled.*Clinic staff will also schedule the DLco and spirometry visit within 2 weeks prior to TV6. These assessments should be performed in an ON state (as reported by the patient to the pulmonary technician) in the pulmonary function facility. As part of the procedure, a slow vital capacity maneuver will be first, followed by DLco, and then spirometry. Clinic staff will arrange to speak with patients by telephone 1 week before TV6 to address any concerns or challenges with the inhaler systems, PD Diary, or Inhaled Dosing Log, to monitor for any AEs, to confirm the DLco and spirometry visit at the pulmonary function lab

has been done/scheduled to confirm the next study visit, to ask the patients how many empty study drug kits will be returned at the next visit, and to remind patients of the study procedures required before the next visit (including completion of the PD Diary and Inhaled Dosing Log).

*Patients who have already completed TV5 at the time of implementation of protocol Version 5.2 will have the option to consent to this amendment at an Unscheduled Visit prior to TV6, at which time they will receive an additional 4 weeks of study drug so that TV6 can be scheduled for approximately 13 months (56 ± 2 weeks) after TV1. These patients will participate in the withdrawal sub-study post-TV6 as described in [Section 10.1.4](#).

10.1.3.9. Treatment Visit 6 for all Patients (13 months [56 ± 2 weeks] or 14 months (60 ± 2 weeks) after TV1)/Early Withdrawal Visit

Treatment Visit 6 will constitute the end-of-study visit. Patients will complete the PD Diary for the 3 consecutive days prior to TV6, and patients will complete the Inhaled Dosing Log daily throughout the treatment period. They will bring their usual PD medications, the PD Diary, Inhaled Dosing Log, used supplies, including empty capsules and inhalers, as well as any unused supplies to the clinic visit. Patients will report to the clinic after having taken their usual PD medications prior to the visit. The timing of administration of the usual morning dose of PD medication may be adjusted by the investigator to accommodate the patient's and/or clinic's schedule. Following their usual morning PD medication, no further non-study PD medications will be used until following completion of all assessments. The timing of arrival should be scheduled to increase the likelihood that patients will be in an ON state upon arrival (i.e., they should arrive to the clinic as shortly as feasible after taking their standard oral PD medications at home).

The following procedures will be done (also refer to [Section 10.1.4](#) for patients entering the withdrawal sub-study):

- Collect, review, sign, and date the PD Diary and Inhaled Dosing Log.
- Collect used empty capsules and inhalers and unused supplies.
- Confirm that the DLco and spirometry visit at the pulmonary function lab was performed within 2 weeks prior to TV6. If these assessments were not completed prior to the visit, the study visit must be re-scheduled.
- Record any changes in the usual PD medication dose/regimen.
- Record the time that patients took their usual PD medications prior to the visit.
- Record any changes in concomitant medications.
- Patient will complete the PDQ-39, PHQ-9, and PGI-C scale in an ON state.
- Complete the UPDRS Part 2 and S&E ADL scales (preferably in the ON state).
- Complete the UPDRS Part 4 (Questions 32-35 and 36-39) (preferably in the ON state).
- Perform the C-SSRS, Epworth Sleepiness Scale, and QUIP (preferably in the ON state).

- Perform a brief physical examination.
- Record standard vital signs (BP, HR, and RR) and orthostatic vital signs (BP and HR).
- Patient will complete the Impact of Parkinson's OFF Episodes Patient Survey (preferably in an ON state)
- Perform a 12-lead ECG.
- Collect blood for clinical laboratory tests including serum pregnancy test, if applicable. Document fasting status.
- The patient will remain in the clinic until they go into the OFF state. After confirmation of an OFF state (between 2 and 5 hours after the patient has taken his/her oral PD medication), record the time of the OFF state. Under clinic staff supervision, patients will prepare and self-administer their entire dose of inhaled study drug (CVT-301 DL1 or CVT-301 DL2).
- Observe the patient for the appearance of dyskinesia and note in the source record if the patient experiences dyskinesia at any time within the 60-minute post-dose period. Also, if applicable, record the maximum severity of the dyskinesia.
- Observe the patient for the occurrence of an ON state during the 60-minute post-dose period and note whether this occurs. If the patient converts to the ON state, note whether or not the patient is still in the ON state at 60 minutes post-dose.
- Monitor patients for AEs throughout the visit.

Once all of the assessments are complete, schedule the patient to undergo a DLco and spirometry visit at the pulmonary lab 4 to 5 weeks after completion of TV6. These assessments should be performed in an ON state (as reported by the patient to the pulmonary technician) in the pulmonary function facility. As part of the procedure, a slow vital capacity maneuver will be first, followed by DLco, and then spirometry.

10.1.4. Sub-Study to Assess Potential Withdrawal Symptoms

After patients are consented to protocol Version 5.2, they will participate in a withdrawal symptom sub-study at the end of TV4, TV5, or TV6, depending on which of the visits is the next scheduled one for the patient. In addition to the assessments detailed in the previous sections for the treatment visit, the AWQ and DDS-PC will be performed upon arrival in the ON state, and the UPDRS Part 1 will be performed preferably in the ON state.

When study activities for the visit are completed, patients will begin a 28-day period of assessment of potential drug withdrawal symptoms. To this end, patients who are at TV4 or TV5 at the time of consent will go on a study drug holiday for this time period. All patients in the withdrawal sub-study (patients consented to protocol Version 5.2) will be given copies of the AWQ, the DDS-PC, PHQ-9, Epworth Sleepiness Scale, C-SSRS (self-report version), and the self-administered MDS-UPDRS Parts 1B and 2 (Movement Disorder Society -UPDRS) to be completed at home at 1, 3, 6, 8, 11, 14, 17, 24, and 28 days after the treatment visit. Patients should fill out the questionnaires during their first ON state (after the intake of their first scheduled dose of standard oral PD medication) on each of these days. The site will call patients

at 14 (± 3) days after the treatment visit to remind them to complete the questionnaires, and to inquire about potential adverse events and changes in concomitant medications. Patients who enter the withdrawal sub-study after TV6 will also receive a call at 28 (± 3) days.

Patients who entered the study drug holiday will be scheduled to return to the clinic for a drug re-supply visit (see [Section 10.1.4.1](#)), and resumption of the full course of study treatment. Patients who entered the withdrawal sub-study after TV6 will be completed with the study after they return the questionnaires and undergo the DLco and spirometry assessment 4 to 5 weeks after completion of TV6, as described in [Section 10.1.3.9](#).

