11.1.9. Serious Adverse Events

A serious adverse event (SAE) is defined as any AE that meets 1 or more of the following criteria:

- The event results in death.
- The event is life-threatening.
- The event is permanently disabling (incapacitating or interfering with the ability to resume usual life patterns).
- The event results in unplanned inpatient hospitalization or prolongation of existing hospitalization.
- The event is a congenital anomaly.
- The event requires medical intervention of any kind in order to prevent any of the aforementioned outcomes.

A serious AE is not necessarily severe; for example, an overnight hospitalization for a diagnostic procedure must be reported as a serious AE even though the occurrence is not medically serious. By the same token, a severe AE is not necessarily serious: for example, nausea of several hours' duration may be rated as severe but may not be considered serious.

An SAE occurring during the study or within 4 weeks of stopping the treatment must be reported to the [REDACTED] and will be communicated to the Sponsor. **Any such SAE due to any cause, whether or not related to the study medication, must be reported within**

24 hours of occurrence or when the investigator becomes aware of the event. [REDACTED]

[REDACTED]

The event must also be recorded on the standard AE eCRF. Preliminary reports of SAEs must be followed by detailed descriptions later on, including clear and anonymized photocopies of hospital case reports, consultant reports, autopsy reports, and other documents when requested and applicable. SAE reports must be made whether or not the investigator considers the event to be related to the investigational drug.

Appropriate remedial measures should be taken to treat the SAE, and the response should be recorded. Clinical, laboratory, and diagnostic measures should be employed as needed in order to determine the etiology of the problem. The investigator must report all additional follow-up evaluations to the [REDACTED] within 10 calendar days. All SAEs will be followed until the investigator and Sponsor agree the event is satisfactorily resolved.

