- ⁹Patients who have already completed TV5 at the time of implementation of protocol Version 5.2 will have the option to consent to this amendment at an Unscheduled Visit prior to TV6, at which time they will receive an additional 4 weeks of study drug.

Appendix 10: Time and Events Table-Treatment Visit (TV6) for all Patients (13 Months [56±2 Weeks or 14 Months [60 ±2 Weeks] after TV1)/ Early Withdrawal Visit

Procedures	Arrival	Pre-dose	Time 0 (Dosing)¹	10 min Post-dose	20 min Post-dose	30 min Post-dose	60 min Post-dose	Post-TV6 DLco/spirometry Assessment
Collect, review, sign and date PD Diary and Inhaled Dosing Log	X							
Collect empty capsules, inhalers, and unused supplies	X							
Pre-TV6 DLco and spirometry assessments ² (within 2 weeks prior to TV6)/confirm complete (and if not re-schedule study visit) ³	X							
Record any changes in usual PD medication dose/regimen	X							
Record time of patient's prior usual PD medication dose	X							
Record any changes in concomitant medication	X							
AWQ and DDS-PC (in ON state)	X ⁴							
PDQ-39 (in ON state)	X							
PHQ-9 (in ON state)	X ⁴							
PGI-C (in ON state)	X							
UPDRS Part 1 (preferably in ON state)	X ⁴							
UPDRS Part 2 (preferably in ON state)	X ^{4,5}							
S&E ADL (preferably in ON state)	X ⁵							
UPDRS Part 4 (Questions 32-35 and 36-39) (preferably in ON state)	X							
Physical examination (brief)	X							
Vital signs (standard BP, HR, and RR and orthostatic BP and HR)	X ⁶							

Procedures	Arrival	Pre-dose	Time 0 (Dosing) ¹	10 min Post-dose	20 min Post-dose	30 min Post-dose	60 min Post-dose	Post-TV6 DLco/spirometry Assessment
Electrocardiogram	X							
C-SSRS (preferably in ON state)	X ⁴							
Epworth Sleepiness Scale (preferably in ON state)	X ⁴							
QUIP (preferably in ON state)	X							
Impact of Parkinson's OFF Episodes Patient Survey (preferably in ON state)	X							
Clinical laboratory tests (including serum pregnancy test, if applicable)	X ⁷							
Self-administration of study drug (in OFF state)			X ¹					
Monitor for dyskinesia and ON/OFF states				X				
Monitor for AEs				X				
Post-TV6 DLco and spirometry assessments ² (at 4-5 weeks after TV6/Early Termination Visit) ³								X
For patients entering the withdrawal sub-study, post-TV6 Telephone contact ⁸								

¹Dosing of study medication preferably occurs between 2 and 5 hours after patient has taken normal morning dose of PD medication and after all pre-dose assessments are complete.

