²DLco and spirometry are to be performed in a dedicated pulmonary facility and includes slow vital capacity maneuver, DLco, and spirometry.

³Patients who withdraw early will undergo all of the TV6 assessments (except the pre-TV6 DLco and spirometry assessment) at the time of withdrawal. They will be scheduled to undergo the post-TV6 DLco and spirometry assessments 4-5 weeks following completion of the Early Withdrawal Visit.

⁴For patients who begin the study drug holiday at the end of this visit. Also dispense copies to be completed at home at 1, 3, 6, 8, 11, 14, 17, 24, and 28 days after TV6/ET. Complete in ON state after intake of first scheduled dose of standard oral PD medication. The self-report version of the C-SSRS and self-administered MDS-UPDRS Parts 1B and 2 will be dispensed for the post TV6 time points.

⁵Preferably in the ON state, but these must be performed before any other study evaluation.

⁶Assessment can be done at any point after arrival and before dosing.

⁷Document whether patient is fasting (≥ 4 hours after last snack or meal).

⁸If applicable, site staff will call the patient at 14 (± 3) days and 28 (± 3) days after TV6/Early Withdrawal to remind them to complete and return the withdrawal questionnaires, and to inquire about potential adverse events and changes in concomitant medications.

**Appendix 11: Time and Events Table-Treatment Visit (TV) 4.1 and TV5.1 for all Patients
(28 days+1 week] after TV4 or TV5)***

Procedures	
Collect completed questionnaires	X
Record any changes in usual PD medication dose/regimen	X
Record any changes in other concomitant medications	X
Record any adverse events	X
Distribute study drug kits	X
Review inhaler training (if needed)	X
Distribute PD Diary and Inhaled Dosing Log; review instructions for completion (if not done at prior visit)	X

*To occur 28 days (+1 week) after TV4 or TV5 (depending on when the patient begins the study drug holiday)

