## Statistical Analysis Plan

- If the start day is missing, the first day of the month will be used.
- If the start day and month are missing, then the first day of the first month (January) will be used.

The original date and time will be shown on all listings of AEs. Listings will be provided for all AEs, serious AEs, AEs leading to study drug discontinuation, AEs leading to dose reduction, and deaths.

TEAEs will be summarized by SOC and PT for each treatment group and CVT-301 overall. TEAEs with onset after the treatment period are attributed to the treatment group during the treatment period. Both event and patient counts, where applicable, will be summarized. The counts will be complemented by percentages will be calculated for the patient counts unless otherwise specified. In addition, the incidence of TEAEs, normalized for duration of exposure to CVT-301 will be presented (number of TEAEs divided by the total exposure to CVT-301, measured as patient years).

- An overall summary of the number and percentage of patients reporting TEAEs and the number of TEAE events, drug-related TEAEs, severe TEAEs, serious TEAEs, TEAEs leading to dose interruption, TEAEs leading to study drug discontinuation, TEAEs leading to dose reduction and TEAEs leading to death
- TEAEs by SOC and PT, both as event and patient counts
- TEAEs by PT, both as event and patient counts
- Drug-related TEAEs by SOC and PT, both as event and patient counts
- Severe TEAEs by SOC and PT, both as event and patient counts
- Drug-related TEAEs by SOC, PT and severity, as event counts; percentages will be calculated for the event count out of total number of events
- Drug-related TEAEs by SOC, PT and relationship, as event counts; percentages will be calculated for the event count out of total number of events
- Serious TEAEs by SOC and PT, both as event and patient counts
- TEAEs leading to study drug interruption, both as event and patient counts
- TEAEs leading to study drug withdrawal, both as event and patient counts
- TEAEs leading to dose reduction, both as event and patient counts
- Most common AEs, both as event and patient counts, most common TEAEs is defined any AE preferred term occurred in greater than 10% total patients
- Time to first onset of most common AEs, classified as 0-1 months, >1-3 months, >3-6 months, >6-9 months and after 9 months, where the date of TEAE onset will be used as the time point for classification

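### Patients who took the drug holiday at TV4 or TV5 have no scheduled adverse-event enquiry after their final dose, although SAEs are reportable for 4 weeks after stopping

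*Protocol*

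**What the plan says.** Protocol 11.1.9 sets the reporting duty without exempting any subset: "An SAE occurring during the study or within 4 weeks of stopping the treatment must be reported".

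Protocol 10.1.4 describes the 28-day withdrawal assessment. It begins at TV4, TV5 or TV6, whichever is the patient's next visit after consent to Version 5.2. For the earlier two visits, "patients who are at TV4 or TV5 at the time of consent will go on a study drug holiday for this time period", after which dosing resumes. All sub-study patients receive a call about 14 days after the visit that opens their own period, "to remind them to complete the questionnaires, and to inquire about potential adverse events and changes in concomitant medications". A second call is reserved: "Patients who enter the withdrawal sub-study after TV6 will also receive a call at 28" (±3) days.

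The TV6/Early Withdrawal schedule in Appendix 10 carries the same limit in its row label, "For patients entering the withdrawal sub-study, post-TV6 Telephone contact". Footnote 8 applies where relevant and places the calls at 14 and 28 (±3) "days after TV6/Early Withdrawal to remind them to complete and return the withdrawal questionnaires, and to inquire about potential adverse events".

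Protocol 10.1.5 gives the 28-day assessments after an early withdrawal only to patients who had not yet taken part in the sub-study.

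On the analysis side, SAP 9.4 states: "TEAEs with onset after the treatment period are attributed to the treatment group during the treatment period".

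**The concern.** The final supervised dose is taken at TV6, which Protocol 10.1.3.9 calls the end-of-study visit, and AE monitoring is listed there for the duration of that visit only. Whether anyone later asks the patient about adverse events depends on which visit happened to come next when the patient consented to Version 5.2. That is an accident of timing and has nothing to do with risk.

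Patients called after TV6 can therefore contribute solicited post-treatment events to the TEAE tables. Patients who had an earlier holiday contribute only what they volunteer. In a long-term safety study to which a withdrawal assessment was deliberately added, events after the final stop should be sought in the same way from everyone. Early withdrawers who have already had their holiday deserve particular notice, because some may be stopping on account of an adverse event. Known events must be followed up (Protocol 8.3 and 11.1.8), but no contact is scheduled to detect new ones.

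**Working it through.** No sample size, power or error rate is involved. The check compares the scheduled contacts with the 28-day window (4 weeks × 7 days).

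**After the final dose, counting from TV6 or Early Withdrawal**

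| Contact | Sub-study starts at TV6/Early Withdrawal | Holiday already taken at TV4/TV5 |
|---|---|---|
| Call at 14 ± 3 days (AE question) | Days 11–17 | none |
| Call at 28 ± 3 days (AE question) | Days 25–31 | none |
| Pulmonary-lab visit at 4–5 weeks (lung tests only) | Days 28–35 | Days 28–35 |
| Scheduled AE enquiries | 2 | 0 |

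Sources: Protocol 10.1.3.9, 10.1.4, 10.1.5 and Appendix 10. The post-TV6 column of Appendix 10 lists DLco and spirometry and nothing else.

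**Do the holiday contacts fill the gap?** Holiday patients are asked about AEs in the call about 14 days after TV4 or TV5. AEs are recorded again at TV4.1/5.1, which falls 4 to 5 weeks after TV4 or TV5. The distance from that visit to TV6 follows from the visit windows:

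- TV5.1: earliest 34 + 4 = week 38, latest 38 + 5 = week 43.
- TV4.1: earliest 22 + 4 = week 26, latest 26 + 5 = week 31.
- TV6 at 60 ± 2 weeks, i.e. weeks 58–62. The gap is 58 − 43 = 15 to 62 − 38 = 24 weeks from TV5.1, and 58 − 31 = 27 to 62 − 26 = 36 weeks from TV4.1.
- TV6 at 56 ± 2 weeks, i.e. weeks 54–58. The gap is 11 to 20 weeks from TV5.1 and 23 to 32 weeks from TV4.1.

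These contacts cover the temporary stop. They end months before the final dose and cannot cover the 4 weeks after it.

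**Does the analysis use these events?** The TEAE definition in SAP 9.4 has a start (first dose after the relevant baseline) and no end date. Events after treatment are assigned to the patient's treatment group, and incidence is also reported as events per patient-year of exposure. A solicited post-treatment event therefore enters the numerator in the called subset, with no matching enquiry in the other.

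**A second, smaller gap.** For the called patients, the ±3 days allows the last call on Day 25, leaving up to 28 − 25 = 3 days of the SAE window without a later enquiry.

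**The case against.** The strongest reply is that every sub-study patient has one actively monitored stop. Holiday patients get a Day 14 call and an in-clinic AE record at TV4.1/5.1, so two AE contacts, the same number as those who enter at TV6. This is correct, and a reader who inferred that holiday patients are never called, or never asked about AEs while off drug, would be wrong. It does not answer the point, because the window in 11.1.9 also runs from the final stop, and that stop is followed up in one subset only.

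Second, Protocol 11.1.8 says the AE question is put at each visit, and SAP 3.8 counts one follow-up visit, so the pulmonary-lab visit might be read as covered. A question at 4 to 5 weeks would indeed look back over the whole window. But no AE item is listed for that visit, it takes place at a dedicated lung-function facility, and the on-site pulmonologist's review (Protocol 11.1.6) concerns the spirometry data. The general rule does not clearly reach it.

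Third, spontaneous SAE reporting still applies to everyone. That stands: what is missing is active enquiry, and the duty to report is intact.

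Fourth, the stop at TV6 might be taken as the longest-exposure withdrawal in the study. For holiday patients exposure was interrupted. With a TV5 holiday over weeks 36–40 and TV6 at week 60, the final stop follows about 60 − 40 = 20 continuous weeks, against about 36 before the holiday. The argument for the call should not rest on exposure length.

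Finally, a reader might extend the point to patients who never consented to Version 5.2. The documents do not support that. Those patients would remain under Version 5.0/5.1, which is not available here, and SAP 4.3 describes home questionnaires after TV6/ET for patients outside the sub-study. Their post-TV6 contacts cannot be judged.

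**Conclusion.** The gap is real for patients who took the holiday at TV4 or TV5, including those who later withdraw early. They have no scheduled AE enquiry after the final dose, against two for patients who start the sub-study at TV6 or Early Withdrawal. This assumes that the general each-visit AE question is not applied at the pulmonary lab, which is the more natural reading of the schedule.

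The consequence is limited. The documents give no split by timing of the holiday, so the number affected cannot be stated. A reader might infer a biased post-treatment incidence or a distorted dose comparison. The SAP plans no separate post-treatment AE table, and nothing shows that holiday timing differs between DL1 and DL2. The likely effect is modest under-ascertainment within the overall TEAE counts. The change is worth making because it is cheap and brings the contact schedule into line with the protocol's own SAE window.

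**What to change.** In Protocol 10.1.3.9, 10.1.4, 10.1.5 and Appendix 10 (the telephone row and footnote 8), apply the existing AE and concomitant-medication call to every patient after TV6 or Early Withdrawal, whenever the holiday was taken. Keep the questionnaire reminder for those completing questionnaires at that time.

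Replace 28 ± 3 days with Day 28 to Day 31, so that the call closes the 4-week SAE window in 11.1.9. The Day 14 call can stay as it is.

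The cost is one short call per affected patient, made by existing site staff with existing content, and a narrower calling window (4 possible days instead of 7). Slightly more post-treatment AEs will be recorded. No treatment rule, endpoint or analysis model changes.
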